3.4 Withdrawal and discontinuation

Each participant will be informed that participation in the investigation is voluntary and that he or she is free to withdraw, without justification, from the investigation at any time without consequences and without affecting professional responsibilities. In case of participant(s) withdrawing their consent to participate in the study, their data and results of tests performed prior to withdrawal will be used by the study team, as stated in the study information provided at recruitment. After termination of the study, the data will be completely anonymized.

Anonymization will be performed with a random number, not associated or related to any personal data or study protocol. The serum sample will be destroyed according to institutional biosafety disposal procedure. Data and samples of study participants who dropped out of the study (no show and no filling out of questionnaires at any follow-up visit) without withdrawing from the study will be used until the time point of drop out, as stated in the study information provided at recruitment, and then stored as described in 7.4.

4 STATISTICS AND METHODOLOGY

4.1. Statistical analysis plan

We consulted a statistician from the CTU Bern ([name]), and we will conduct the study in collaboration with the department of statistics of the CTU Bern. In 2019, the police department of the canton of Bern listed 2'491 fulltime equivalents [24]. Nix et al. examined response rates to 497 police surveys reported in 390 articles published in 15 journals from 2008 to 2017, and found a mean response rate of 64.3% (St. Dev. 25.9) [27]. Because our survey includes serum sampling, we estimated a conservative voluntary study participation of 25% (i.e., approx. 625 individuals). We also performed a pre-study survey within the police department, and 927 individuals confirmed their interest to participate. Hence, this pre-study investigation corrects our sampling size estimate to 1'000 study participants.

For the primary endpoint, we hypothesize that the COVID-19 seroprevalence within the police department will be between 1% and 2% at the beginning of the study. We further hypothesize that the seroprevalence will increase during the study period by 8% (i.e., from 2% to 10%). A precision-based sample size calculation will be applied to reduce the margin of error.

Considering the uncertainty from the serological survey and including our validation results and

the manufacturer's data, we calculate a sensitivity of 97% and a specificity of ≥99% for detecting SARS-CoV-2 antibodies in serum [28].

Proportion, %	CI width (%) for				
	800 Participants	1000 Participants	1200 Participants	1400 Participants	1600 Participants
1%	15	13	12	11	10
2%	20	18	16	15	14
3%	24	21	20	18	17
4%	27	24	22	21	19
5%	30	27	25	23	21
6%	33	30	27	25	23
7%	36	32	29	27	25
8%	38	34	31	28	27
9%	40	36	32	30	28
10%	42	37	34	31	29

Reading example: Including 1200 participants yields a CI 13.4 to 29.6%, given a true proportion of 2%.

The Table demonstrates sample size consideration to derive the precision (width of 95% confidence interval, CI) for a specific seroprevalence achieved when the corresponding number of policemen of Kanton Bern is included into the prospective cohort study using serological testing. The Wilson method was used to calculate CIs.

At every visit, we will first calculate the crude seroprevalence as the proportion of the seropositive samples among all collected samples. Second, we will adjust the seroprevalence for test characteristics (false positive and false negative rate). Third, we will calculate the weighted seroprevalence to adjust for sampling imbalances, with weighting factors based on the demographic structure of the police force (age, sex, rural vs. city distribution). We will furthermore analyze changes in seropositivity in a repeated-measures mixed-effects logistic regression model. In a second step, we will include health-related, activity-related and geography-related risk factors as covariates into the model to study effects of these factors and derive corresponding odds ratios. Change of risk factors over time will be accounted for. The change of antibody titres over time will also be analyzed using mixed models.

In addition to demographic characteristics, a descriptive analysis of health-related variables (i.e. diabetes, arterial hypertension, cardiovascular disease, chronic pulmonary disease, immunocompromised status because of host diseases or medical treatment, cancer, obesity), and activity-related data (i.e. fieldwork activity vs office and administration activity, working in cities or rural areas) will be performed. The categorization of variables is illustrated in appendix 2. Comparison of categorical and continuous variables will be performed with chi-square tests, t-tests, Wilcoxon-Mann-Whitney-Test, Kruskal-Wallis-Test and multivariate analysis, accordingly. The significance level will be two-sided $\alpha = 0.05$.

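### The precision table and its reading example are ten times too large: the widths labelled as percent are per mille, and the example interval excludes the 2% it is built on

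*Combined protocol and SAP*

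**What the plan says.** Section 4.1 (Statistical analysis plan) announces the approach: "A precision-based sample size calculation will be applied to reduce the margin of error". The hypotheses for the primary endpoint are that seroprevalence "will be between 1% and 2% at the beginning of the study" and that "the seroprevalence will increase during the study period by 8% (i.e., from 2% to 10"%. The planned size is 1000: "this pre-study investigation corrects our sampling size estimate to 1'000 study participants".

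A table follows, with proportions of 1% to 10% in the rows and 800 to 1600 participants in the columns. Its header gives the interval widths in percent, and the entries run from 10 to 42. The example reads "Reading example: Including 1200 participants yields a CI 13.4 to 29.6%, given a true proportion of 2"%. The note under the table describes the entries as the "width of 95% confidence interval, CI" and names the method: "The Wilson method was used to calculate CIs". No other section gives a per-mille unit or corrects the scale.

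**The concern.** The example contradicts itself. An interval of 13.4% to 29.6% cannot come from a Wilson calculation at 2%, because that interval always contains the proportion put into it. The 2% row of the table carries the same problem: a width of 16 for 1200 participants is the distance from 13.4 to 29.6 (29.6 − 13.4 = 16.2).

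This table is the plan's only precision figure, and it concerns the primary endpoint. Taken as printed, 1000 participants would give an interval 18 points wide at 2%. Since its lower limit cannot be below 0, its upper limit would be at least 18%, beyond the hypothesised end-of-study value of 10%. An ethics committee, funder or reader who relied on the table would conclude that the first objective cannot be answered at this size.

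**Working it through.** **Inputs, all from section 4.1.** 95% level; significance level two-sided at 0.05; Wilson method; p = 1% to 10%; n = 800, 1000, 1200, 1400, 1600. z = 1.96.

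**Formula (Wilson score interval, no continuity correction).**

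- centre = (p + z²/2n) / (1 + z²/n)
- half-width = z · √(p(1−p)/n + z²/4n²) / (1 + z²/n)

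**Step 1: the plan's own example, p = 0.02, n = 1200.**

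- z²/n = 0.003201; z²/2n = 0.001601
- centre = (0.02 + 0.001601) / 1.003201 = 0.02153
- half-width = 1.96 × √(0.00001633 + 0.00000067) / 1.003201 = 0.00806
- limits = 0.01348 and 0.02959, that is 1.35% to 2.96%, width 1.61 percentage points

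In per mille this is 13.48 to 29.59. The printed 13.4 to 29.6 is therefore the right interval in per mille with a percent sign attached. (The lower limit appears to have been truncated; rounded, it would be 13.5.)

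**Step 2: the whole table.** Wilson widths in percentage points, with the printed entry in brackets:

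| p | n = 800 | 1000 | 1200 | 1400 | 1600 |
|---|---|---|---|---|---|
| 1% | 1.45 (15) | 1.29 (13) | 1.17 (12) | 1.07 (11) | 1.00 (10) |
| 2% | 1.99 (20) | 1.77 (18) | 1.61 (16) | 1.49 (15) | 1.39 (14) |
| 3% | 2.40 (24) | 2.14 (21) | 1.95 (20) | 1.80 (18) | 1.68 (17) |
| 4% | 2.74 (27) | 2.45 (24) | 2.23 (22) | 2.07 (21) | 1.93 (19) |
| 5% | 3.04 (30) | 2.72 (27) | 2.48 (25) | 2.29 (23) | 2.14 (21) |
| 6% | 3.31 (33) | 2.96 (30) | 2.70 (27) | 2.50 (25) | 2.33 (23) |
| 7% | 3.55 (36) | 3.17 (32) | 2.90 (29) | 2.68 (27) | 2.51 (25) |
| 8% | 3.77 (38) | 3.37 (34) | 3.08 (31) | 2.85 (28) | 2.66 (27) |
| 9% | 3.98 (40) | 3.55 (36) | 3.24 (32) | 3.00 (30) | 2.81 (28) |
| 10% | 4.17 (42) | 3.72 (37) | 3.40 (34) | 3.15 (31) | 2.94 (29) |

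The unrounded width × 1000 rounds to the printed integer in 50 of 50 cells (largest difference 0.499). The width × 100, the unit in the header, matches in 0 of 50.

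**Step 3: could another method explain it?** In percent, Wald, continuity-corrected Wilson and Clopper-Pearson intervals also match 0 of 50 cells. In per mille they match 40, 6 and 14. Only plain Wilson in per mille reproduces the table.

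**Step 4: what it means at the planned n = 1000.**

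| p | 95% CI | Width (points) | Printed |
|---|---|---|---|
| 1% | 0.54% to 1.83% | 1.29 | 13 |
| 2% | 1.30% to 3.07% | 1.77 | 18 |
| 10% | 8.29% to 12.02% | 3.72 | 37 |

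The intervals at 2% and 10% are more than 5 points apart (8.29 − 3.07 = 5.22).

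**The case against.** **A per-mille sign may have been misread.** If the authors worked in per mille, a misread sign in the extracted text would give exactly this pattern. That cannot be excluded without the original page, and a look at it settles the matter. But the misreading would have to occur in both the table header and the example, while the percent sign beside 2 in that same example makes sense. Lost decimal points do not explain it either, because the example keeps its decimals.

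**The table does not set the sample size.** This is correct. The figure of 1000 comes from feasibility: 2491 full-time equivalents, a first estimate of 25% participation, then 927 people who confirmed interest. No target width is stated. The table is the only precision justification, not the origin of the number.

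**The harm is limited.** The impossible example warns an attentive reader, the named method lets anyone recover the scale, and the error understates precision, so it hides no undersized study. All true, and it bears on the consequences; the statement is still wrong as written.

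**The corrected widths are not the precision of the adjusted estimate.** This also stands. The table ignores the adjustment for test error and the weighting planned in section 4.1. With the stated sensitivity of 97% and, as an assumption, specificity at the stated floor of 99%, a true 2% gives an apparent prevalence of 0.02 × 0.97 + 0.98 × 0.01 = 2.92%. The crude Wilson width at n = 1000 is then 2.11 points, and dividing by 0.97 + 0.99 − 1 = 0.96 gives 2.20. At 10% the apparent prevalence is 10.6%, and the width is 3.82 / 0.96 = 3.98 points. This takes the test characteristics as known and leaves out weighting. The change from 1.77 and 3.72 is small beside a factor of 10.

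**Conclusion.** The point holds. All 50 widths, and both limits of the example, are ten times too large in the unit printed. True widths across the table run from 1.00 to 4.17 percentage points, against 10 to 42 as printed. The fault is one of unit: the Wilson calculation itself is sound, and 1000 participants is enough to separate 2% from 10%. The correction is still required, because the plan's only precision statement for its primary endpoint is impossible as written and leads a reader to the opposite conclusion about the study's size. The result rests on the level and method named in section 4.1 and on the percent signs being in the original page. The corrected figures are crude Wilson widths for a single visit with complete data.

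**What to change.** 1. Check the original page for the unit printed in the table header and in the example.
2. Divide all 50 entries by 10 and label them as percentage points (at 1000 participants: 1.3, 1.8 and 3.7 for 1%, 2% and 10%). Alternatively, keep the integers and label the widths clearly as per mille.
3. Replace the example with: *Including 1200 participants yields a 95% CI of 1.35% to 2.96% (width 1.61 percentage points), given an observed proportion of 2%.* It should say observed rather than true, because the calculation treats 2% as the sample proportion.
4. Add one sentence saying that the widths are for crude seroprevalence, before adjustment for test error and weighting, and that 1000 was set by expected participation.

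The cost is a correction to one table and a few sentences. Recruitment, visits, testing and analysis do not change.

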4.2. Handling of missing data

Questionnaires will be screened for completeness. In case of missing data, study participants will be contacted by the study team to verify missing data. In the final analysis, we will use all available data. Mixed models implicitly account for missing data as long as at least one measurement per participant is available.

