2.2 Primary and secondary endpoints

Primary endpoint: The variable of primary interest is **COVID-19 seropositivity**. This variable is measured at five time points over the one-year study period. The following baseline factors may have an influence on the primary endpoint and will be obtained: (i) pre-existing comorbidities, (ii) rural versus city distribution of working place, and (iii) office work versus field work.

Secondary endpoints: We will assess the proportion of symptomatic and asymptomatic cases among seropositive participants. We will calculate the attack rate in different subgroup. These include (i) study participants with health-related risk factors (age>50 and age>60 years, diabetes, arterial hypertension, cardiovascular disease, chronic pulmonary disease, immune-compromised status due to host diseases, medical treatment, cancer, obesity), (ii) activity-related subgroups (i.e. fieldwork vs office activity), (iii) geography-related subgroups (i.e. city vs rural areas). In follow-up visits, the antibody titers (i.e. dynamic) and the neutralization capacity will be assessed. Thereby we will determine the change in serum levels of SARS-CoV-2 antibodies over time in seropositive participants.

2.3 Project design:

This is a single center special population (i.e. police officers of the canton of Bern) seroprevalence survey. It is a repeated cross-sectional investigation in the canton of Bern combined with a longitudinal cohort study with serial sampling of the included study participants. The protocol is aligned with the one of seroprevalence studies recommend by the WHO [25].

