In serum samples with positive antibody test, quantification of neutralizing antibodies will be performed at the IFIG. They will be measured by pre-incubating serial dilutions of baseline and convalescent serum with 200 to 400 plaque forming units (PFU) of SARS-CoV-2, after which a PFU reduction assay will be performed on Vero-E6 cells. After 2 days, cells will be fixed and stained with crystal violet to analyse the neutralizing capacity of antibodies generated towards SARS-CoV-2, as previously described [26].

The results of Anti-SARS-CoV-2-Test of will be communicated to study participant via e-mail within 2 weeks of blood sampling. The results of neutralization capacity will be communicated at the end of the study period. This experimental assay will be performed in the research laboratory with all positive samples during one month, at the end of the study period.

Seropositive participants or participants with a positive SARS-CoV-2 test in the past (PCR or antigen test) will be asked to complete an additional questionnaire that investigates possible contacts (i.e., working versus private environment) and sources of transmission (see point 5 in the BASEC application: "CASE REPORT FORM").

Seropositive participants or vaccinated participants will be contacted by the study team within 4 weeks after laboratory result, for one additional blood sampling that investigates neutralization capacity. Seropositive participants with vaccination will be contacted twice. Figure 2 illustrates the sampling scheme.

Antibodies	Vaccine	No. of blood sampling in 1 year
		
negative	no	5 baseline + every 3 months
positive	no	6 baseline + every 3 months + 1 sampling
negative	yes	6 baseline + every 3 months + 1 sampling
positive	yes	7 baseline + every 3 months + 2 samplings

Figure 2: Schematic overview of the blood sampling over one year

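### The missing-data statement in section 4.2 does not cover the visit-wise seroprevalences, which would be biased if attendance at visits 2–5 depends on an earlier result

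*Combined protocol and SAP*

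**What the plan says.** Section 2.2: "The variable of primary interest is" seropositivity, and "This variable is measured at five time points over the one-year study period".

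Section 4.1 describes two separate analyses of it.

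- **Visit-wise prevalence.** "At every visit, we will first calculate the crude seroprevalence as the proportion of the seropositive samples among all collected samples". Next, "Second, we will adjust the seroprevalence for test characteristics (false positive and false negative rate"). Third come weights built from age, sex and urban or rural post.
- **Change over time.** A mixed-effects logistic regression is then added for changes in seropositivity, with risk factors entered as covariates.

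Section 4.2 has participants contacted about gaps in their questionnaires and then states: "In the final analysis, we will use all available data". It adds: "Mixed models implicitly account for missing data as long as at least one measurement per participant is available". Section 3.4 keeps the data of dropouts up to the point of dropout. None of this says how a missed blood sample is handled in the prevalence at that visit.

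Section 3.3 says that antibody results "will be communicated to study participant via e-mail within 2 weeks of blood sampling", while visits are three months apart. Seropositive participants also receive an additional questionnaire and additional blood sampling.

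**The concern.** Two things are missing. Section 4.2 gives a condition (one measurement per participant) that lets a person enter a mixed model but does not make the model valid under missing data. The condition needed is missing at random given the earlier results and covariates in the model, with the model correctly specified.

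The visit-wise prevalences, moreover, are not outputs of that model. A proportion among attenders uses nobody's earlier results. The design hands each participant a result before the next visit and asks more of those who test positive, so attendance could plausibly depend on a status the study has already recorded. Data can then be missing at random given the history while the visit-wise proportion is still biased. The planned weights contain no serostatus, so they cannot undo it.

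At stake are the prevalences at visits 2–5, the first analysis described for the primary endpoint.

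**Working it through.** **1. The plan's own precision figure.** Section 4.1 tabulates Wilson 95% widths. With z = 1.96, the limits are [p + z²/2n ± z√(p(1−p)/n + z²/4n²)] / (1 + z²/n). At n = 1000:

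- p = 2%: 1.30% to 3.07%, width 1.77 points (table: 18).
- p = 10%: 8.29% to 12.02%, width 3.72 points (table: 37).

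The table agrees when its entries are read per 1000; its % label is a separate matter. The 10% interval serves as a yardstick.

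**2. Inputs.** From the documents: five visits, 2% rising to 10%, 1000 participants, sensitivity 97%, specificity 99% (stated as at least 99%). Assumed: a linear path 2/4/6/8/10%; seropositivity persists once acquired; attendance is a₁ if the last result was positive and a₀ if it was negative. Attendance therefore depends only on recorded results (missing at random). Steps 3 and 4 ignore test error.

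**3. Permanent dropout.** A share of 0.02 of the cohort is first positive at each visit k = 1 to 5, and attends visit 5 with probability a₀^(k−1)·a₁^(5−k). The 0.90 who stay negative attend with probability a₀⁴.

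- 70%/90%: positives 0.0048 + 0.0062 + 0.0079 + 0.0102 + 0.0131 = 0.0422; negatives 0.90 × 0.6561 = 0.5905. Crude = 0.0422/0.6327 = 6.68%.
- 95%/80%: positives 0.0163 + 0.0137 + 0.0116 + 0.0097 + 0.0082 = 0.0595; negatives 0.90 × 0.4096 = 0.3686. Crude = 0.0595/0.4281 = 13.89%.

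**4. Intermittent absence.** Entering visit 5, the true 10% splits into positives already found (K) and not yet found (U). From visit 2 on, U is 0.02 new plus (1−a₀) times the previous U.

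- 70%/90%: U = 0.0200, 0.0220, 0.0222, 0.0222, so K = 0.0778. Attending positives 0.0778 × 0.7 + 0.0222 × 0.9 = 0.0744; negatives 0.90 × 0.9 = 0.81. Crude = 0.0744/0.8844 = 8.42%.
- 95%/80%: U = 0.0200, 0.0240, 0.0248, 0.0250, so K = 0.0750. Attending positives 0.0913; negatives 0.72. Crude = 0.0913/0.8113 = 11.25%.

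**5. Effect of the planned adjustments.** Rogan-Gladen correction (97%, 99%) and post-stratification over two equal strata (assumed to end at 12% and 8%), under permanent dropout, gave 6.69% at 70%/90% and 13.88% at 95%/80%. The bias remains.

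**6. Using the history.** Under permanent dropout, weighting each attender by 1/[a₀^(k−1)·a₁^(5−k)], or 1/a₀⁴ for those still negative, restores each 0.02 and the 0.90, giving 0.10/1.00 = 10.0%. A simulation of 2,000,000 persons agreed. A single-visit weight on last serostatus, fitted among all enrolled, does not work here: someone lost early stays last seen negative although they may have converted since.

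| Visit 5, truth 10% | Crude | Single-visit weight | Cumulative weight |
|---|---|---|---|
| Permanent, 90/90 | 10.0% | 8.9% | 10.0% |
| Permanent, 70/90 | 6.68% | 8.9% | 10.0% |
| Permanent, 95/80 | 13.89% | 8.0% | 10.0% |
| Intermittent, 70/90 | 8.42% | 10.0% | not needed |

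**7. Scale.** Smaller gaps matter less: under permanent dropout, 85%/90% gives 9.04% and 80%/90% gives 8.17%. Fewer than 1000 attend visit 5, so the yardstick is generous. With 633 attending (70/90), the approximate half-width is 1.96√(0.09/633) = 2.3 points against an error of 3.3. With 428 (95/80), it is 2.8 against 3.9. Both intermittent cases stay inside the 8.29% to 12.02% interval.

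**The case against.** The strongest reply is that the plan does not use these proportions for change over time: section 4.1 gives that to the mixed model, and the sentence in 4.2 is about mixed models and never claims to cover the proportions. A reader might infer that the hypothesised rise from 2% to 10% is to be read off the visit-wise figures, and that the primary estimate of trend is therefore biased. The documents do not support this. They name seropositivity as the variable of primary interest, label no estimate as primary, and assign change to the model.

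The documents also give no attendance or dropout rate, so the differential, its size and its sign are assumed. The trigger is only partly specific to serostatus: results are e-mailed to everyone, and vaccinated antibody-negative participants are also asked for an extra draw. Visit 1 is untouched, and absence explained by age, sex or geography alone is handled by the planned weights.

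A tempting shortcut also overstates the effect. Applying the lower attendance to everyone currently positive gives, at 70%/90%, 0.07/0.88 = 8.0%. But recent converters have not yet been told of a positive result. If 8% are known and 2% new, the figure is (0.056 + 0.018)/(0.074 + 0.81) = 8.4%. Letting unobserved status drive attendance would not be missing at random.

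All of this limits what may be claimed. What stands is that nothing in the plan protects the visit 2–5 prevalences if attendance follows earlier results, and that 4.2 omits the condition its own model needs.

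**Conclusion.** The point holds as a conditional one. If attendance at visits 2–5 depends on an earlier result already given to the participant, the crude, test-adjusted and weighted prevalences at those visits are biased even under missing at random, and the planned weights cannot repair it. With equal attendance there is no bias.

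Size and direction cannot be derived from the documents. The illustrations at visit 5 run from 6.68% to 13.89% against a true 10%. They rest on assumed 15- to 20-point attendance gaps, a linear rise and persistent seropositivity, and the largest errors need permanent dropout. The mixed model of change is a separate analysis, valid only under missing at random and a correct model. This is worth correcting before analysis; it does not show that the study's results will be wrong.

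**What to change.** 1. **Section 4.2.** Replace the mixed-model sentence with: the mixed models are valid if data are missing at random given earlier serostatus and the model covariates, and if the model is correctly specified.
2. **Section 4.1.** Beside the crude figure, report visit 2–5 prevalences that use each participant's serostatus history. Use inverse-probability-of-attendance weights from a parsimonious model (last serostatus, vaccination, age, sex, geography), multiplied by the post-stratification weight. For permanent dropout the weight must be the cumulative product of visit-specific probabilities; for intermittent absence, visit-specific weights suffice. State how participants are classed between the two. Multiple imputation from the history is an equivalent route.
3. **Sensitivity analysis.** Shift non-attenders' prevalence over a range fixed in advance: overall prevalence = (share attending × prevalence in attenders) + (share absent × shifted prevalence).
4. **Reporting.** Show attendance at each visit by last serostatus, so that readers can see whether the problem arose.

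The cost is SAP text and modest programming. No visit, sample or procedure changes, and the inputs are already planned data or needed for the sampling scheme. The downsides are somewhat wider confidence intervals and a sparse attendance model early on: at 2% of 1000, about 20 participants enter visit 2 with a positive result, so the model must stay small.
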